5 STUDY POPULATION

5.1 Inclusion Criteria

In order to be eligible to participate in this study, a subject must meet all of the following criteria at the screening and Day 1 visits, unless specified otherwise:

1. Male or female subject, 18 years of age or older, at the time of consent.
2. Subject has a history of moderate to severe CHE for at least 6 months prior to baseline. (information obtained from medical chart or subject's physician, or directly from the subject).
3. Subject has hand eczema refractory to moderate potency, high potency or ultra-high potency topical corticosteroids (defined in [Table 3](#)) or systemic corticosteroids (including oral or injectable corticosteroids) used in the past year (information obtained from medical chart or subject's physician, or directly from the subject). Refractory is defined by failure to achieve a status of clear, almost clear or mild CHE following at least a 2-week course of moderate potency, high potency or ultra-high potency topical corticosteroid or systemic corticosteroids (including oral or injectable corticosteroids).
4. Subject has moderate to severe CHE at Day 1, as defined by a hand PGA 3 or 4.
5. Subject has been using an emollient on their hands and feet (if foot eczema is present) (except those containing urea or salicylic acid) every day at the same frequency for at least 1 week prior to Day 1 and agrees to continue using that same emollient, daily and at the same frequency, throughout the study. Note: On the day of scheduled visits, subjects cannot apply emollient before their scheduled visit time on their hands and feet.
6. Subject has a body mass index (BMI) $\leq 38 \text{ kg/m}^2$.
7. For female subject of childbearing potential involved in any sexual intercourse that could lead to pregnancy: the subject must agree to use a highly effective contraceptive method from at least 4 weeks before Day 1 until at least 4 weeks after the last study product administration. Highly effective contraceptive methods include hormonal contraceptives (e.g. combined oral contraceptive, patch, vaginal ring, injectable, or implant), intrauterine devices or intrauterine systems, vasectomized partner(s), tubal ligation, or double barrier methods of contraception (e.g. male condom with cervical cap, male condom with diaphragm, or male condom with contraceptive sponge) in conjunction with spermicide.

Note: Subjects must have been on a stable dose of hormonal contraceptives for at least 4 weeks before Day 1.

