5.2 Exclusion Criteria

A subject who meets any of the following criteria at the screening and Day 1 visits, unless specified otherwise, will be excluded from participation in this study:

1. Subject is a female who is breastfeeding, pregnant, or who is planning to become pregnant during the study.
2. Subject has known allergic contact dermatitis of the hands or hands and feet and is unable to avoid exposure to the causative allergen.
3. Only for subjects with a history of atopic dermatitis (clinically confirmed diagnosis according to Hanifin and Rajka criteria ([APPENDIX C](#))): the atopic dermatitis is covering > 15% of the BSA at baseline (Day 1) (excluding hands and feet)
4. Only for subjects with a history of atopic dermatitis (clinically confirmed diagnosis according to Hanifin and Rajka criteria ([APPENDIX C](#))): subject had a flare in his atopic dermatitis in the last 4 weeks prior to the screening visit.
5. Subject has active skin infections of the hands and/or feet.

6. Subject has a history or has current active psoriasis.
7. Subject has a history of erythrodermic, refractory or unstable skin disease, including AD, that requires frequent hospitalizations and/or frequent intravenous treatment for skin infections over the last year
8. Subject has a history of eczema herpeticum within 12 months, and/or a history of 2 or more episodes of eczema herpeticum in the past.
9. Subject has a history of skin disease or presence of skin condition that, in the opinion of the investigator, would interfere with the study assessments.
10. Subject has a history of cancer or lymphoproliferative disease within 5 years prior to Day 1.
Note: Subjects with successfully treated nonmetastatic cutaneous squamous cell or basal cell carcinoma and/or localized carcinoma in situ of the cervix are not to be excluded.
11. Subject has any clinically significant medical condition or physical/laboratory/ECG/vital signs abnormality that would, in the opinion of the investigator, put the subject at undue risk or interfere with interpretation of study results.
12. Subject has 12-lead ECG abnormalities considered by the investigator to be clinically significant or a QTcF \geq 450 milliseconds, regardless of clinical significance, at screening. Abnormal ECG may be confirmed with one repeated assessment. For subjects with a QTcF \geq 450 msec on initial ECG, the mean of the two QTcF values will determine eligibility.

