Extent of disease will be assessed at the visits specified in [Table 1](#) and will be estimated by the physician as the percentage of hand area (palmar and dorsal) affected by eczema, both hands (both surface) cumulating 100%.

Extend of Disease will be analyzed as follows:

- Change and percent change from baseline in Extent of Disease affected with moderate to severe CHE at all visits with assessments scheduled

Modified Total Lesion Symptom Score (mTLSS) Feet

For exploratory purposes, a separate mTLSS will be evaluated for the feet for subjects for which the presence of foot eczema will be documented at the screening and Day 1 visits. Scores will be assigned for the most affected side (plantar or dorsal) of the most affected foot. Only subjects with foot involvement at baseline will be part of these analyses.

Foot mTLSS will be analyzed as follows:

- Change and percent change from baseline in foot mTLSS at all visits with assessments scheduled from Weeks 4 to Week 32

Physician's Global Assessment (PGA) Feet

For exploratory purposes, a separate PGA will be evaluated for the feet, for subjects for which the presence of foot eczema will be documented at the screening and Day 1 visits. Only subjects with foot involvement at baseline will be part of these analyses.

Foot PGA will be analyzed as follows:

- Proportion of subjects achieving at least a 2-grade reduction from baseline to clear (0), almost clear (1) or mild (2) in foot PGA at all visits with assessments scheduled from Weeks 4 to Week 32
- Proportion of subjects achieving a foot PGA of clear (0) or almost clear (1) at all visits with assessments scheduled from Weeks 4 to Week 32
- Change from baseline in foot PGA at all visits with assessments scheduled from Weeks 4 to Week 32

Extent of Disease for Subjects Affected with Foot Eczema

PPD	STATISTICAL ANALYSIS PLAN, Version Final 1.0
Protocol Number: ASN002AD-202 V6.0	Sponsor: Asana BioSciences, LLC

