Presence or absence of foot eczema will be assessed at the visits specified in [Table 1](#) must be documented in the source document and eCRF. For exploratory purposes, a separate extent of the disease will be evaluated for the feet, for subjects for which the presence of foot eczema will be documented at the visits specified in [Table 1](#). Percentage will be estimated by the physician as the percentage of foot area (plantar and dorsal) affected by eczema, both feet (both surface) cumulating 100%. Only subjects with foot involvement at baseline will be part of these analyses.

Analyzes will be done as follows:

- Change and percent change from baseline in Extent of Disease affected with foot eczema at all visits with assessments scheduled from Weeks 4 to Week 32

Validated Investigator Global Assessment (for Subjects with AD only)

For subjects with AD only, disease severity (excluding hands and feet) will be assessed at the visits specified in **Error! Reference source not found.**, before the study product administration, using the validated Investigator Global Assessment scale for atopic dermatitis (vIGA-AD). The vIGA is a global assessment of the current state of the disease. It is a 5-point morphological assessment of overall disease severity. The condition will be documented in the eCRF along with the vIGA scores recorded at the visits specified in Table 1.

Analyzes will be done using:

- Proportion of subjects achieving at least a 2-grade reduction from baseline to clear (0) or almost clear (1) in vIGA at Weeks 4 and 16.
- Proportion of subjects achieving at least a 2-grade reduction from baseline in vIGA at Weeks 4 and 16.
- Change from baseline in vIGA at Weeks 4 and 16

Exploratory Analysis

Change and/or percent change in hand mTLSS by CHE subtype, pruritus score portion of mTLSS, WPAI-SHP, Extent of Disease, foot mTLSS and foot PGA will be presented using descriptive statistics by visit and initial treatment group for both parts of the study. Analyses will be based on the mITT population.

PPD	STATISTICAL ANALYSIS PLAN, Version Final 1.0
Protocol Number: ASN002AD-202 V6.0	Sponsor: Asana BioSciences, LLC

For categorical efficacy endpoints involving proportions based on foot PGA and vIGA, counts and percentages will be presented for each visit.

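### The foot PGA and vIGA responder endpoints have no minimum baseline grade, so they can count unchanged subjects as responders and subjects who cannot respond as failures

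*SAP*

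**What the plan says.** **Hand.** Protocol 5.1 sets a floor: "Subject has moderate to severe CHE at Day 1, as defined by a hand PGA 3 or 4". Every subject starts with room for a 2-grade fall, and nobody starts at 0/1.

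**Foot.** SAP 13.3 carries the two hand responder definitions over to the feet. One is "Proportion of subjects achieving at least a 2-grade reduction from baseline to clear (0), almost clear (1) or mild (2) in foot PGA". The other is "Proportion of subjects achieving a foot PGA of clear (0) or almost clear (1) at all visits with assessments scheduled", which asks for no reduction from baseline. Both come from protocol section 3. The analysis set is defined by this sentence: "Only subjects with foot involvement at baseline will be part of these analyses". Protocol 5.1 and 5.2 contain no criterion on the severity of foot eczema.

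**AD.** The SAP adds two vIGA responder endpoints: "Proportion of subjects achieving at least a 2-grade reduction from baseline to clear (0) or almost clear (1) in vIGA" and "Proportion of subjects achieving at least a 2-grade reduction from baseline in vIGA at Weeks 4 and 16". On who is assessed it says: "For subjects with AD only, disease severity (excluding hands and feet) will be assessed". The AD entry rules in protocol 5.2 set upper limits only. A subject is excluded if AD covers more than 15% of body surface outside the hands and feet at Day 1, or if the "subject had a flare in his atopic dermatitis in the last 4 weeks prior to the screening visit".

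**Presentation.** SAP 13.3 shows the foot PGA and vIGA proportions as counts and percentages, without a test. Change from baseline is also listed for foot PGA and for vIGA. The Section 8 baseline table includes hand PGA and vIGA, but not foot PGA.

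**The concern.** A responder definition is informative only if each subject starts outside the response and is able to reach it. The hand entry criterion guarantees both. Presence of foot eczema, or of AD, guarantees neither.

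On the PGA scale (protocol Table 7, also used for feet), grade 1 still requires at least one mild sign, so a subject can have foot eczema at grade 1. On the vIGA scale (protocol Appendix D), grade 0 is the absence of inflammatory signs. That is possible in a subject with a history of AD, or with AD confined to the hands and feet, which this vIGA excludes.

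Efficacy on foot eczema is a stated exploratory objective, and these two responder rates are among its endpoints. A clear/almost clear rate that contains subjects who never changed is hard to read, as is a 2-grade rate whose denominator contains subjects who could not change. The two foot rates are pushed in opposite directions by the same subjects.

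**Working it through.** The documents give no figure for these endpoints to reproduce. The only sample-size statement (SAP 5.1) concerns the primary endpoint and has no bearing here.

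**Step 1: which baseline grades can meet which endpoint.** Both scales run from 0 to 4. The cells give the post-baseline grades that count as a response.

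| Baseline grade | Foot 0/1: met at Day 1? | Foot 2-grade | vIGA 2-grade to 0/1 | vIGA 2-grade |
|---|---|---|---|---|
| 0 | (no foot eczema) | none | none | none |
| 1 | yes | none | none | none |
| 2 | no | 0 | 0 | 0 |
| 3 | no | 0, 1 | 0, 1 | 0, 1 |
| 4 | no | 0, 1, 2 | 0, 1 | 0, 1, 2 |

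Only the foot 0/1 endpoint can be met at Day 1. Foot PGA 1 and vIGA 0 or 1 can never meet a 2-grade endpoint.

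**Step 2: effect on the rates.** Let f be the share of analysed subjects at foot PGA 1 (or at vIGA 0/1), equal in each arm. Let p be the response rate among the others, and q the share of foot PGA 1 subjects who are at 0/1 at the visit.

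- 2-grade rate = (1 − f)·p, so the difference = (1 − f)·(p_active − p_placebo).
- Foot 0/1 rate = (1 − f)·p + f·q, so the difference = (1 − f)·(p_active − p_placebo) + f·(q_active − q_placebo).

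**Step 3: numbers.** Assumed, because the documents give none of these: p = 20% on placebo and 50% on active (true difference 30 points), and q = 100% in both arms.

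| f | 2-grade, placebo vs active | Foot 0/1, placebo vs active | Difference (points) |
|---|---|---|---|
| 0 | 20% vs 50% | 20% vs 50% | 30 |
| 10% | 18% vs 45% | 28% vs 55% | 27 |
| 20% | 16% vs 40% | 36% vs 60% | 24 |
| 30% | 14% vs 35% | 44% vs 65% | 21 |
| 50% | 10% vs 25% | 60% vs 75% | 15 |

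**Step 4: when q differs between arms.** This matters for foot 0/1 only.

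- With f = 30%, the same p, and q = 70% on placebo and 90% on active: 0.7·0.2 + 0.3·0.7 = 35% vs 0.7·0.5 + 0.3·0.9 = 62%, a difference of 27 points rather than 21.
- With f = 30%, p = 10% vs 40%, and q = 60% vs 95%: 0.7·0.1 + 0.3·0.6 = 25% vs 0.7·0.4 + 0.3·0.95 = 56.5%, a difference of 31.5 points against a true 30. Here it does not shrink.

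**Step 5: unequal f.** Randomization is stratified by biopsy collection and hand PGA, not by foot eczema or AD, so f can differ between arms by chance. Take no drug effect, p = 30% in both arms, q = 100%, and f = 10% on active and 40% on placebo.

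- 2-grade: 0.9·0.3 = 27% vs 0.6·0.3 = 18%, active minus placebo +9 points.
- Foot 0/1: 0.27 + 0.10 = 37% vs 0.18 + 0.40 = 58%, active minus placebo −21 points.

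With no drug effect at all, the two foot endpoints would then point in opposite directions.

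**The case against.** The strongest reply is that little depends on these tables. They are exploratory and untested. The foot objective is also served by change in foot PGA and by change and percent change in foot mTLSS and foot extent, none of which uses a responder cut-off. Baseline vIGA is already tabulated, so a reader can see how many AD subjects could not respond. All of this stands and keeps the priority low. It does not cover foot PGA, whose baseline distribution is not tabulated.

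Several stronger readings are tempting, and the documents do not support them.

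- *Subjects meet response at Day 1 on all these endpoints.* This is true of foot 0/1 only; the other three require a reduction.
- *The entry criteria remove active AD, so many AD subjects start at vIGA 0 or 1.* The criteria cap extent and exclude a recent flare; AD on up to 15% of body surface is allowed. The flare rule is timed to screening, while baseline vIGA is taken on Day 1, up to 30 days later and after treatment washouts. Appendix D grades marked signs of limited extent as moderate. Low baseline grades are permitted, but their frequency is unknown.
- *The treatment difference always shrinks.* For foot 0/1 it need not, as Step 4 shows. Keeping near-clear feet near clear can itself be a drug effect.
- *A separate AD question is answered wrongly.* The SAP states no AD objective; it lists the vIGA endpoints beside the foot-eczema objective.

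One may also ask why the floor should be 2 when hand entry requires 3 or 4. A grade-2 subject can meet a 2-grade endpoint only by clearing completely. A floor of 2 removes only subjects for whom the outcome is fixed in advance or already met, and keeps the most data. A floor of 3 would match the hand more closely, at the price of smaller numbers.

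**Conclusion.** The point holds in a limited form. The plan's rules admit foot PGA 1 subjects, who satisfy foot 0/1 before dosing and can never satisfy the foot 2-grade endpoint, and AD subjects at vIGA 0 or 1, who can never satisfy either vIGA endpoint. This follows from the definitions alone.

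The size is unknown because f is not given. With equal f in each arm, the loss on the 2-grade endpoints is exactly the fraction f of the true difference: 3 to 15 points of an assumed 30 for f between 10% and 50%. On foot 0/1, subjects who did not change raise the rates. The difference falls by the same fraction only if grade-1 subjects stay at 0/1 equally often in each arm. A chance imbalance in f can move results either way.

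The effect is confined to descriptive exploratory tables. The primary endpoint and the hand PGA endpoints are not touched.

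**What to change.** - In SAP 2 and 13.3, compute the foot PGA 0/1, foot PGA 2-grade and both vIGA responder proportions in subjects with a baseline grade of 2 or higher on the relevant scale, and show the resulting N per arm. With f = 0, the assumed rates in Step 3 return to 20% vs 50%.
- Write the vIGA denominator out. Appendix 1 defaults to the whole population per arm unless otherwise specified, and the vIGA text has no analysis-set sentence like the one for the feet.
- Keep the change-from-baseline summaries in all subjects with foot involvement or AD.
- Add baseline foot PGA to the Section 8 table.
- Record the restriction in SAP 3.5, since the foot endpoints come from the protocol.

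The cost is SAP wording and a denominator flag built from Day 1 data already collected. Because the flag is defined at baseline, the comparison between randomized arms is preserved. The downside is smaller denominators in descriptive tables.

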14 SAFETY ANALYSIS

All safety analyses will be conducted using the safety population and will be presented combined except adverse events, which will be presented separately for Part A and Part B. For both parts subjects will be presented by their initial treatment as assigned in Part A.

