^d Including height, weight and BMI. Height will be measured only at screening and the same value will be used for BMI calculation at other visits.

^e ECG will be recorded at 0 (pre-dose, within 1 hour prior to dosing), 1 (\pm 30 min), and 3 (\pm 1 hour) hours post-dose on Day 1, Week 4, Week 16 and Week 20. ECG will be recorded only once at screening, Weeks 8, 24 and 32 and ET visit (if applicable).

^f Only at ET

^g If PPD is used, a second screening visit will be necessary.

^h mTLSS, Extent of Disease and PGA to be assessed only for hands and feet, but evaluated separately.

ⁱ Microbiome samples will be collected for all subjects prior to tape stripping collection and skin biopsy (if applicable). Microbiome samples will be collected on Day 1, Week 4 and Week 16 (or ET visit, if applicable) (one from lesional skin (palmar aspect (when possible) of the worst hand) and one from adjacent nonlesional skin). At each visits samples should be collected from the same areas selected on Day 1. Microbiome samples should be collected prior to study product administration and after photographs, if applicable. If the subject has presence of foot eczema on Day 1, microbiome samples (lesional and non lesional) will be collected from the plantar aspect (when possible) of the worst foot.

^j Only at ET, if ET visit is performed prior to Week 16.

^k Skin tape stripping samples will be collected for all subjects as close as possible to the site of microbiome collection (preferably the same palmar lesion when possible) and of the skin biopsy (if applicable). Skin tape stripping samples will be collected on Day 1 (one from lesional skin and one from adjacent nonlesional skin) and one at Week 4 and Week 16 (or ET visit, if applicable) (from same lesional area as Day 1). Tape stripping should be collected prior to study product administration and after photographs, if applicable. If the subject has presence of foot eczema on Day 1, skin tape stripping samples will also be collected from the foot (one from lesional skin and one from adjacent nonlesional skin) at Day 1 and one at Week 4 and Week 16 (or ET visit, if applicable) from same lesional skin as Day 1.

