^l Optional, only for a subset of approximately 36 subjects who consent: two 2.5-mm skin biopsies at Day 1 (one from lesional skin and one from adjacent nonlesional skin) and one at Week 16 (or ET visit, if applicable) (from the same lesional skin as Day 1) and preferably from the same lesion as the one selected for the microbiome and tape stripping sampling. Biopsies are collected from the palmar aspect of the hand and should be collected adjacent to the tape stripping site. Subjects consenting to biopsies collection must also consent to PD samples. Biopsies should be collected prior to study product administration and after photographs, if applicable.

^m An additional skin biopsy from same lesional skin as Day 1 (and adjacent from the tape stripping site) and PD sample will be collected at Week 4 for subjects who consent to four biopsies.

ⁿ Optional, only for a subset of approximately 36 subjects who consent: PD samples to be drawn as trough samples prior to study product administration. Subjects consenting to PD samples must also consent to biopsies. PD samples should be collected prior to study product administration.

Study Visits	Screening	Treatment Period											Follow-up / ET
		Part A						Part B					
Day (D); Week (W)		D1	W2 (D15)	W4 (D29)	W8 (D57)	W12 (D85)	W16 (D113)	W18 (D127)	W20 (D141)	W24 (D169)	W28 (D197)	W32 (D225) EOT ^a	W36 (D253) EOS
Window (days)	-30 to -1		±1	±1	±2	±2	±2	±2	±2	±2	±2	±2	±2

^o PK samples will be collected at 0 (pre-dose), 2 (± 30 min) hours post-dose and 6 hours post-dose (between 5 to 12 hours post-dose). The dosing time for the previous day should be recorded accurately.

^p PK samples will be collected at 0 (pre-dose) and 2 (± 30 min) hours post-dose. The dosing time for the previous day should be recorded accurately. At ET visit (if applicable), only one PK sample will be collected.

^q Study products will be taken at home daily for 32 weeks, except on study visit days when the study products will be administered on site. For visit Week 18, subjects will dose at home.

^r Emollient use must be initiated at least 1 week prior to Day 1.

^s On this visit, subject who were receiving placebo since Day 1, will start receive ASN002 80 mg until EOT visit.

^t Subject should be instructed to always bring their medication to the site when there is a scheduled visit.

^u On Week 2 visit, there will be no collection/dispensing, but subject will dose on site with the medication kit dispensed on Day 1.

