2.1.2 ASN002

ASN002 is an orally bioavailable, potent dual inhibitor of JAK and SYK kinases with 50% inhibitory concentrations (IC50 values) of 5-46 nM in biochemical assays. In cell-based

mechanistic assays, the compound showed inhibition of IgE-immune complex induced degranulation and phosphorylation of LAT (Linker for Activation of T cells) a substrate of SYK, and also IL-6 induced phosphorylation of STAT3 (IC₅₀ range 14–143 nM). In a collagen-induced arthritis model, ASN002 demonstrated a significant reduction in arthritic, histopathology and radiographic scores when compared to vehicle. The compound also showed broad antiproliferative activity in a panel of cell lines representing both solid and leukemia/lymphoma tumor types. The data from both in vitro (cell line) and in vivo efficacy studies with ASN002 provide strong rationale for its evaluation in the treatment of inflammatory disorders, such as CHE. In a Phase 1b study (ASN002AD-101), plasma concentrations of ASN002 were measured in subjects with AD following single and repeated once daily oral administration at 20, 40 and 80 mg. At steady state, C_{max} and AUC were dose dependent with approximately 1.5-fold or less accumulation compared to those on Day 1, and the mean elimination t_{1/2} were 7.3–13.7 hours. At 80 mg, the mean C_{max} and AUC_{tau} of ASN002 at steady state were 252 ng/ml and 3340 ng*hr/ml, respectively. The safety and tolerability profile of ASN002 at all dose levels was excellent in that Phase 1b study. The most common adverse event (AE) observed was transient, mild headache, mostly restricted to Day 1 likely due to fasting. There were no clinically significant laboratory changes including hematological parameters observed in this study. ASN002 showed robust clinical efficacy with nearly all patients obtaining a 50% improvement in disease severity (EASI₅₀) at 40 mg and 80 mg once daily and substantial decreases in patient-reported itch measured by Numeric Rating Scale (NRS) after 4 weeks of treatment.

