6 TREATMENT

6.1 Study Treatment Administered

This study involves two different doses of ASN002 (40 mg and 80 mg) both orally administered once daily compared to a placebo in Part A (first 16 weeks of treatment). Then, only active products (ASN002 40 mg and 80 mg) will be administered in Part B. ASN002 will be available in 20-mg strength tablets. All study products will be provided by the sponsor. All study products will be self-administered orally, at home or at the clinic on clinic visit days.

Study products administration will occur daily for 32 weeks at approximately every 24 hours, on an empty stomach (2 hours before and 2 hours after a meal) with approximately 240 mL of water. On visit days, the study products will be administered at the study center, except at Week 18. The date and time of the drug administration and fasting conditions will be collected by the study site on the visit days. When dosing at home, the subject will be instructed to take the study product at approximately the same time of the day and compliance will be self-reported during each study visits.

Further details regarding the study products for Part A can be found in [Table 2](#).

Table 2. Study Products

	Study Products		
Product name	ASN002	ASN002	Placebo (Part A only)
Dosage form	Tablet	Tablet	Tablet
Dosage level(s)	40 mg	80 mg	N/A
Unit dose strength(s)	20 mg	20 mg	N/A
Number of tablets per dose level	2 active and 2 placebo	4 active	4 placebo
Route of administration	Oral	Oral	Oral
Dosing instructions	Once a day with approximately 240 mL of water	Once a day with approximately 240 mL of water	Once a day with approximately 240 mL of water
Source of procurement	Asana BioSciences, LLC	Asana BioSciences, LLC	Asana BioSciences, LLC

The contents of the label will be in accordance with all applicable regulatory requirements.

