4.3 Safety Population

The safety population will include all subjects who received at least one dose of the study product. All subjects will be analyzed according to the treatment that they actually received in Part A.

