14.4 Electrocardiogram (ECG)

Descriptive statistics will be presented for data related to ECGs (heart rate, RR interval, PR interval, QRS duration, QT interval and QTcF interval). Change from baseline values will be presented for each post-baseline assessment.

Shift tables from baseline to each post-baseline visit and to each timepoint describing shifts to abnormality will be provided for overall interpretation. Only subjects with a baseline result and a result at the specified visit will be considered.

A listing of ECG assessments will be provided. In addition, a listing will be provided for each parameter where a subject had at least one abnormal result.

PPD	STATISTICAL ANALYSIS PLAN, Version Final 1.0
Protocol Number: ASN002AD-202 V6.0	Sponsor: Asana BioSciences, LLC

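### Placebo-start subjects' Week 16 post-dose ECGs follow their first ASN002 80 mg dose but are summarised by initial treatment, so that visit has no valid post-dose placebo reference

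*SAP*

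**What the plan says.** Five provisions bear on this point.

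- **ECG timing.** Protocol section 1.3, Table 1, footnote e, requires ECGs pre-dose (within 1 hour before dosing) and at 1 and 3 "hours post-dose on Day 1, Week 4, Week 16 and Week 20". The other on-treatment ECG visits (Weeks 8, 24 and 32) have a single recording.
- **Start of active drug.** Footnote s, attached to dispensing at Week 16, reads: "On this visit, subject who were receiving placebo since Day 1, will start receive ASN002 80 mg until EOT visit". Table 1 places Week 16 under Part A.
- **Place of dosing.** Protocol section 6.1: "On visit days, the study products will be administered at the study center, except at Week 18".
- **Treatment label.** SAP section 14 combines the two parts for all safety data except adverse events, and adds: "For both parts subjects will be presented by their initial treatment as assigned in Part A". SAP section 4.3 says of the safety population: "All subjects will be analyzed according to the treatment that they actually received in Part A". SAP section 6.7 and Appendix 1 put crossover subjects in a column headed Placebo/ASN002 80mg.
- **ECG summaries.** SAP section 14.4 gives change from baseline for each post-baseline assessment, and: "Shift tables from baseline to each post-baseline visit and to each timepoint describing shifts to abnormality will be provided for overall interpretation".

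For combined outputs by treatment and visit, Appendix 1 also says that the two 80 mg columns are anchored to the first dose time. It does not define that term.

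**The concern.** Both labelling rules work at the level of the subject: a person carries one treatment label, taken from Part A, through every table. At Week 16 the treatment changes within a single visit, between the pre-dose ECG and the 1 h ECG. A subject-level label cannot record that change.

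Week 16 is the end of the placebo-controlled period. Apart from Day 1 and Week 4, it is the only Part A visit with ECGs after a dose. ECG change is a named secondary safety endpoint. Someone reading the Week 16 1 h and 3 h rows will naturally take the placebo-start column as the comparator for the two active arms, because the schedule shows Week 16 as a Part A visit. In those rows the comparator is itself on ASN002 80 mg. A drug effect on heart rate, PR or QTcF would be present in all three columns and would look smaller than it is.

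**Working it through.** **1. Is the Week 16 dose the first active dose?** The Week 16 visit is nominally Day 113. Days 1 to 112 are 112 daily doses, and 112 / 7 = 16 weeks, the full length of Part A. The dose on Day 113 is therefore the first of Part B. Footnote s starts ASN002 80 mg at this visit, new product is dispensed there, and dosing is on site. The 1 h and 3 h ECGs follow that dose; the pre-dose ECG precedes it.

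**2. How many readings?** Scheduled Part A ECGs in the placebo arm, taking Day 1 pre-dose as baseline:

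| Visit | Timepoints | Post-baseline | Post-dose | After ASN002 |
|---|---|---|---|---|
| Day 1 | 0, 1, 3 h | 2 | 2 | 0 |
| Week 4 | 0, 1, 3 h | 3 | 2 | 0 |
| Week 8 | single | 1 | 0 | 0 |
| Week 16 | 0, 1, 3 h | 3 | 2 | 2 |
| Total | | 9 | 6 | 2 |

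So 2 of 9 post-baseline readings, 2 of 6 post-dose readings, and both post-dose readings at Week 16 are on active drug. Seven of nine remain true placebo readings.

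**3. How many subjects?** The plan wants 25 per group after 25-30% dropout and enrols up to 35. Its figure reproduces: 25 / (1 - 0.25) = 33.3, rounded up to 34, and 25 / (1 - 0.30) = 35.7, rounded up to 36; 35 lies between. Conversely, 35 x 0.75 = 26.25 and 35 x 0.70 = 24.5. About 24 to 26 placebo subjects would reach Week 16 and cross over.

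**4. Does any other rule separate these readings?**

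- SAP section 14.1 splits adverse events, and section 10 splits medications, at Week 16 by date or visit. Neither rule covers ECGs, and neither could divide readings taken on the same day.
- The Placebo/ASN002 80mg heading shows that a crossover occurs, but not that it falls between two timepoints of the Week 16 visit.
- The anchor in Appendix 1 has two readings. If it means the first study dose, Week 16 stays Week 16 and nothing moves. If it means the first ASN002 dose, the 1 h and 3 h readings become first-dose 80 mg data. The text does not choose.
- Protocol section 9.3.3 tabulates ECGs by treatment and visit, without mention of timepoint. Pooling within the visit would mix the clean pre-dose reading with the other two.

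**5. Direction of the distortion.** The only relevant figure in the documents is from the Phase 1b study: steady-state exposure "with approximately 1.5-fold or less accumulation compared to those on Day 1". Assume that the ECG effect is proportional to concentration without delay, that exposure at 40 mg is half that at 80 mg, and that accumulation R lies between 1.0 and 1.5. Set the first-dose 80 mg effect to 1. The steady-state effect is then R at 80 mg and R/2 at 40 mg, and the share of the true effect left in the Week 16 post-dose contrast is:

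- 80 mg: (R - 1) / R
- 40 mg: (R/2 - 1) / (R/2) = 1 - 2/R

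| R | 80 mg | 40 mg |
|---|---|---|
| 1.0 | 0% | -100% |
| 1.25 | 20% | -60% |
| 1.5 | 33% | -33% |

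The 80 mg contrast keeps at most a third of any true effect, and the 40 mg contrast reverses sign. If ASN002 has no ECG effect, nothing is distorted.

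**The case against.** The case for leaving the plan alone has real substance.

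- **The last placebo ECG is clean.** A reader might infer that the final on-placebo ECG reference is lost. It is not: the Week 16 pre-dose ECG is that reference, and the Day 1 and Week 4 post-dose ECGs also stand. This limits the point to one visit's post-dose readings.
- **The column discloses the crossover.** A reader might infer that on-drug values will appear under a bare Placebo heading. The documents do not support that for ECGs. SAP section 14 presents them combined, so the heading is Placebo/ASN002 80mg. The first lock is for efficacy, and SAP section 3.4 says that the Part A safety cleaning involves no interim statistics. Disclosure in a heading still does not tell the reader which Week 16 rows are on drug.
- **Appendix 1 may already cover it.** Anchoring to the first ASN002 dose is a natural reading for a combined 80 mg column. It is not the only one, so the objection shows what needs defining and does not remove the need.
- **Nothing is tested.** Protocol section 9.3.3 rules out inferential statistics on safety variables, and no arm-versus-placebo ECG difference is planned. Each subject's change from baseline is also calculated correctly. This stands in full. The harm is to how a descriptive table is read.
- **The timepoint shift tables are narrow.** They cover the overall ECG interpretation. For QTcF, PR and heart rate, the point rests on the descriptive change-from-baseline summaries.

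**Conclusion.** The point holds within narrow limits. As written, the SAP summarises the Week 16 1 h and 3 h ECGs of about 24 to 26 placebo-start subjects by initial treatment, although those readings follow a first ASN002 80 mg dose. The count rests on 35 per group and the planned 25-30% dropout. Only the Week 16 post-dose reference is affected.

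The bias is towards hiding a drug effect on the ECG. That direction needs only that an effect, if there is one, appears within 1 to 3 hours of the first dose. The percentages in the working need more: linearity in concentration, dose-proportional exposure (the protocol says only that exposure was dose dependent), and the reported accumulation. They are bounds under assumptions, not estimates. The documents give no size for any QTcF, PR or heart-rate effect, so a figure in milliseconds would be hypothetical. No hypothesis test or error rate is involved.

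**What to change.** Amend SAP sections 14 and 14.4 and Appendix 1 so that, for subjects randomised to placebo:

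1. ECG readings are assigned by date and time relative to the subject's first ASN002 dose.
2. The Week 16 pre-dose reading is shown as the last placebo value.
3. The Week 16 1 h and 3 h readings are shown as first-dose ASN002 80 mg, and are not used as placebo reference in descriptive summaries or shift tables.
4. Timepoints within the Week 16 visit are kept separate and never pooled.
5. For the Combined ASN002 80mg column, first dose time is defined as the first ASN002 80 mg dose.

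This keeps the combined layout of SAP section 14, as long as that section names the exception to presentation by initial treatment. The cost is a few SAP sentences and a timepoint flag in programming; data collection, visits and dosing do not change. The one loss is a placebo post-dose ECG reference at Week 16, which the design does not provide anyway.
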